6. STUDY DESIGN

a. Overall design

This is an open label, randomized, phase 3 study designed to compare romiplostim plus dexamethasone vs dexamethasone alone in terms of sustained response off any ITP treatment in adult subjects (≥18 years old) with newly diagnosed of ITP.

According to the International Working Group assessment [1] patients will be screened for study participation. Subjects who meet eligibility criteria will be enrolled. Once eligibility is confirmed, patient will be randomized, Randomization will be stratified by center with a 1:1 allocation using random block sizes, to receive dexamethasone 40 mg daily x 4 days only in the first cycle and subcutaneous romiplostim weekly for up to 12 months (ROM + DEX arm) or dexamethasone 40 mg daily x 4 days for up to 3 cycles every 14 to 28 days (DEX arm).

The monitoring will be the same in both arms with slight differences to allow for dose adjustments of romiplostim:

- In the ROM + DEX arm, patients will be reviewed weekly for 8 weeks (56 days). After week 8, patients will be reviewed every 2 weeks (14 days) for 8 additional weeks and then monthly until week 52 (365 days) from randomization.
 - o If romiplostim dose should be modified, patients will be reviewed weekly until a stable dose of romiplostim is reached for at least 4 weeks (28 days). After that, patients will go on with visits every 2 weeks (14 days) for 8 weeks and then monthly until Week 52 (365 days) from randomization.
- In the DEX arm, patients will be reviewed weekly until the completion of dexamethasone cycles and for a minimum of 8 weeks (56 days). After that,

every 2 weeks (14 days) for 8 additional weeks and then monthly until Week 52 (365 days) from randomization.

The following assessments will be done in these visits: platelets count, bleeding score, number and characteristics of bleeds, adverse events, study medication, rescue medication and concomitant medication, HRU associated with the ITP or its treatment and lost productivity (days of absentee in scholarship or work and presentism).

Quality of life will be evaluated at Day 1 (the day of administration of the first dose), Month2 (Day 60), Month 6 (Day 180) Month12 (Day 365) and End of study Visit (visit 12 months after the last dose of study treatment). See Study schedule for more details.

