In the DEX arm, if platelet counts are lower than 20x10⁹/L or bleeding symptoms related to thrombocytopenia are present between cycles, rescue therapy with IVIg (maximum dose 2 gr/kg during 1 to 5 days) or low doses of prednisone (0,5 mg/kg/d) could be used. If patients use rescue treatment with prednisone low doses, they should be decreased as soon as possible in a maximum of 8 weeks. It would be considered treatment failure if platelets are lower than 30x10⁹/L after 3 cycles of dexamethasone or rescue medication is needed to get this level of platelets despite the 3 cycles of dexamethasone.

Once romiplostim or dexamethasone is stopped or after 365 days since randomization, patients should be clinically evaluated minimum every 4±1 weeks for 6 months (180 days) and continuation of treatment should be decided on an individual basis by the treating physician. If patient needs treatment again it will be prescribed according to routine clinical practice. If romiplostim is used, it will not be supported by the sponsor.

At specified visits outlined in the Study Schedule, patients will undergo physical exams including measurement of vital signs (respiratory rate, body temperature, blood pressure, and pulse rate), height (only at screening visit) and weight, blood counts with absolute and relative differential (neutrophil, lymphocyte and monocyte)blood chemistry profiles (serum creatinine, ALT, AST, GGT, K, Na, LDH), platelet counts, haemoglobin counts as well as review of adverse events and serious adverse events. Measurements of treatment response, health-related quality of life, and other measurements of efficacy per SOC will be collected.

In this study approximately 126 patients will participate. They will be enrolled in 30 study sites from Spain, United Kingdom and Italy.

b. Primary endpoint

Primary outcome measure:

To evaluate the difference between study arms in the proportion of patients achieving 6mSROT-50 at 6 months (180 days) from treatment cessation.

 Definition of 6mSROT-50: platelets higher or equal than 50x10⁹/L in the absence of any ITP treatment including any rescue treatment for at least 6 consecutive months (≥180 days) from treatment cessation and without WHO grade 2 or more bleeding.

c. Secondary endpoints

Secondary outcome measures:

- To evaluate the difference between study arms in the proportion of patients achieving 6mSROT-30 at 6 months (180 days) from treatment cessation.

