	 If stable dose is 1mcg/kg/14 days after 4 doses stop romiplostim 					
Platelets >250x10 ⁹ /L	Stop romiplostim and platelet control weekly.					
	 Restart romiplostim when platelets < 150x10⁹/L 					
	 Restart romiplostim at 1mcg/kg/weekly less than previous 					

- 1. The starting dose should be 3 mcg/kg/week*. It could be start during de 4 days of dexamethasone. This dosage is due to:
 - The patient profile, on whom it is urgent to achieve an effective treatment as soon as possible.
 - Current clinical practice. PTI Spanish clinical guideline [43] recommends starting with a dose of 5-10 mcg/kg in urgent cases. In the Spanish PTI guideline also it is stated that "although Romiplostim is initiated according to prescribing information at a dose of 1 μg/kg/week subcutaneously, most patients require doses of 3 μg/kg/week to respond, so in clinical practice it is usually initiated at 3 μg/kg/week, reaching a maximum dose of 10 μg/kg/week."
 - Other clinical study [44] with similar patient profiles the median dose (Q1-Q3) of romiplostim was 2,6(1,6-3,9)mcg/kg.

*Since the starting dose of romiplostim will be 3 mcg/kg instead of 1 mcg/kg as indicated in the label, close monitoring of potential safety concerns will be conducted.

- 2. Patients will weekly receive dose increases of romiplostim in increments of 1 mcg/kg up to a maximum dose of 10 mcg/kg in an attempt to reach a target platelet count higher than 50x10⁹/L.
 - If romiplostim dose is stable for 4 weeks and platelets are higher than 50x10⁹/L, romiplostim will be tapered in 1 mcg/kg per week up to a dose of 1 mcg/kg per week.
 - If after 4 additional weeks patients still present platelet counts higher than 50x10⁹/L with romiplostim 1 mcg/kg, romiplostim will be indicated as 1 mcg/kg/14 days.
 - If after 4 doses of romiplostim 1 mcg/kg/14 days, platelets remain still higher than 50x10⁹/L treatment with romiplostim should be ended.
- 3. Otherwise, if platelets are lower than 50x10⁹/L treatment with romiplostim will go on until Day 365 since randomization.

If platelets are between 50-100x10⁹/L, investigator will take the decision to stop or not romiplostim according to patient's risk of bleeding. This decision will be always taken after discussion with the study coordinator.

Dexamethasone

Dexamethasone will be given to the patient for oral administration at home.

In the ROM + DEX arm, dexamethasone will be administered 40 mg daily x 4 days only in the first cycle

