- In the DEX arm, if platelet counts are lower than 20x10⁹/L or bleeding symptoms related to thrombocytopenia are present between cycles, rescue therapy with IVIg (maximum dose 2 gr/kg in total during 1 to 5 days) or low doses of prednisone (0,5 mg/kg/d) can be used. If patients use rescue treatment with prednisone, they should be decreased as soon as possible and stopped within 8 weeks.

f. Treatment failure

In the ROM + DEX arm, it would be considered treatment failure if platelets are lower than 30x10⁹/L after 4 weeks with romiplostim at 10 mcg/kg/week or rescue

medication is needed to get this level of platelets despite this dose of 10mcg/kg/week for 4 weeks.

In DEX arm, it would be considered treatment failure if platelets are lower than 30x10⁹/L after 3 cycles of dexamethasone or if rescue medication is needed to get this level of platelets despite the 3 cycles of dexamethasone.

In both arms, treatment failure will be considered to in those patients bleeding who are refractory to therapy in whom it is considered clinically in their best interests to escalate or switch treatment in a way that does not align with the protocol treatment schedules. Patients will be discussed with Steering Committee before to be considered treatment failure.

If patients lose response on the DEX arm, they can be switched from one arm to the other (to TPO-RA), but outside the trial. The treatment will be provided by their centre and this information will be collected up in the CRF. The patients will be considered a treatment failure.

g. Accountability

The study medication (i.e., romiplostim, dexamethasone) will be sent directly from the sponsor to the investigator's site pharmacy preceded by the Regulatory Green Light. The medication is to be used exclusively in the clinical trial according to the instructions of this study protocol.

When a drug shipment is received, the Investigator or designee will check the amount and condition of the delivery, drug expiration date, and sign the Receipt of Shipment Form provided. The Receipt of Shipment Form should be faxed or sent by e-mail to the CRO. The original form will preliminarily be retained at the site and will be collected at the next monitoring visit by the monitor and stored in the TMF at CRO. A copy will remain in the Investigator File at the site. In case of shipment problems, the Investigator or designee shall contact the CRA as soon as possible.

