An Investigational Product Accountability Log will be provided for the trial medication. The record must be continuously updated and contain the dates, quantities and compounds of drugs received, medication identification number(s), the patient identification number to whom the trial medication was dispensed, date and quantity of medication dispense and the initials of the dispenser.

h. Concomitant medication

Throughout the study, investigators may prescribe any concomitant medications or treatments deemed necessary to provide adequate supportive care, except for those listed in section *Prohibited drugs*.

For concomitant therapies therapy name, indication, dose, unit, frequency, route, start date and stop date will be recorded.

Reduction or discontinuation of permitted concurrent ITP therapies may begin once a subject's platelet count has increased to ≥50x10⁹/L.

Rescue medication will also be collected.

Concomitant therapies are to be collected from screening through the EOS visit, as applicable.

i. Prohibited drugs

The following medications are not permitted during this study. After treatment failure, they will be allowed:

- Other thrombopoietic receptor agonists
- Any cytotoxic agents, alkylating agents
- Rituximab
- rHuTPO
- Interferon
- Herbal supplements that are associated with bleeding side effects including, but not limited to, gingko biloba, garlic, ginseng, fish oil, dong quai, feverfew. Garlic and ginseng taken through a normal diet are not excluded.
- Aspirin at doses higher than 100mg or anticoagulant drugs.
- Treatments for ITP other than allowed rescue medications (includings plenectomy).
- Any other investigational agents that are not approved

Should a subject require administration of any of the medications listed above, sponsor should be consulted before the medication is administered, when possible. In all cases, sponsor must be informed within 24 hours. Sponsor may decide that the subjects will be ineligible to receive additional administrations of study medication.

STUDY SCHEDULE AND STUDY FLOW-CHART

Study flow-chart

[figure not shown]

Table 3. Schedule of study assessments.

DEX arm

Visit number	Visit 0 Screening	Visit 1 Baseline	Visit 2- 8	Visit 9	Visit 10, 11, 12, 13 and 15	Visit 17-18	Visit 19	Visit 20-24	Visit 25	Visit 26-36 (Periodical clinical evaluation after the end of study medication ¹¹)	Visit 37 (End of study Visit) ¹²	

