11. STATISTICAL CONSIDERATIONS

a. General considerations

The statistical analysis plan will be developed and finalized before database lock.

Descriptive statistics will be obtained for all variables: mean, median, standard deviation and range, Q1, Q3, and CI 95% for continuous variables, and frequencies and percentages for categorical variables.

Summary statistics will be provided by treatment groups for disposition, demographics, baseline characteristics, exposure to investigational product, adverse events, concomitant medication, labs and clinical outcome assessment data.

A Chi- square test or Fisher test if applicable will be used to compare categorical variables between groups. Time-to-event variables will be estimated by the Kaplan-Meier method from the randomisation. The log-rank test will be used to compare the survival curves. All the other endpoints will be compared between the two arms with appropriate statistical tests. All statistical tests will be two-sided with an α -level of 0.05.

b. Sample size

The primary endpoint of this study is the 6mSROT-50 (≥50x10⁹/L) rate at 6 months from treatment cessation. In patients with newly diagnosed primary immune thrombocytopenia

^b Listing for reconciliation should include all ICSRs submitted to Amgen Safety per contract (for studies in Table 2 listing should contain SUSARs, pregnancy and lactation exposure (and any associated reports/outcomes), USADEs, SADEs and non-serious ADEs).

treated with dexamethasone 40 daily x 4 days for one to three cycles, 6mSROT-50 (≥50x10⁹/L) at 6 months from treatment cessation has been assumed to be 30% [2]. The sample size was based on the assumption that ROM + DEX can improve sustained response at 6 months from treatment cessation up to 56.6% similarly to eltrombopag plus dexamethasone as described by Zhang [2]. A total of 63 patients/arm are required to achieve 80% power to detect a difference with a two-sided significance level of 5%, if the true 6mSROT-50 rates at 6 months from treatment cessation are 30% in the DEX arm and 56,6% in the ROM + DEX arm and assuming a dropout rate of 15%. The total minimal size is 126 patients to be randomized.

c. Analytical Populations

Safety Population

The safety population will consist of all randomized subjects who received at least one dose of study treatment. Subjects will be analysed according to the treatment actually received. Analysis for safety endpoints will use this analysis set.

ITT Population

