All patients who are randomized will be included in the ITT Population. The ITT Population will be used to summarize subject disposition and baseline characteristics. Patients will be analysed according to the treatment they were allocated to at randomization; not necessarily the treatment they actually received. Results will be presented "as randomized."

mITT Population

All patients who are randomized and received at least one dose of study medication will be included in the mITT Population. The mITT Population is the primary analysis population for efficacy. Patients will be analysed according to the treatment they were allocated to at randomization; not necessarily the treatment they actually received. Results will be presented "as randomized."

rITT Population

All patients who are randomized and received at least one dose of study medication and achieved response (R) at any time during the study will be included in the rITT Population. The rITT Population will be used for the analysis of time to loss of response. Patients will be analysed according to the treatment they were allocated to at randomization; not necessarily the treatment they actually received. Results will be presented "as randomized."

d. Analysis of Primary Objective

The primary endpoint is 6mSROT-50 rate at 6 months (180 days) from treatment cessation.

The proportion of patients with 6mSROT-50 and corresponding 95% CIs for each study arm will be provided. A Chi-square test or Fisher test if applicable, will be used to compare the proportion of 6mSROT-50 between treatment arms.

e. Analysis of Secondary Objectives

i. Secondary Efficacy evaluations

For the analysis of the secondary endpoints, following analyses will be conducted:

- The proportion of patients with 6mSROT-30, 12mSROT-30 and 12mSROT-50 and corresponding 95% CIs for each study arm will be provided. A Chi-square test or Fisher test if applicable will be used to compare the proportion of each endpoint between treatment arms.
- The proportion of patients with CR, R, GR or TR at 6 and 12 and End of study Visit (visit 12 months after the last dose of study treatment) will be calculated and corresponding 95% CIs for each study arm will be provided. A Chi-square test or Fisher test if applicable will be used to compare the proportion of each endpoint between treatment arms.

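### 6mSROT-50 does not count a declared treatment failure as non-achievement, leaving a route to primary success after salvage therapy that is essentially confined to ROM+DEX

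*Protocol*

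**What the plan says.** The primary endpoint (Protocol 1.j and 6.b) needs platelets of at least 50x10⁹/L "in the absence of any ITP treatment including any rescue treatment for at least 6 consecutive months (≥180 days) from treatment cessation" and no WHO grade 2 or worse bleeding. 6mSROT-30 and the two 12-month versions (6.c) have the same structure. Treatment cessation is not defined. Treatment failure appears only as a separate secondary outcome. Section 11.d fixes the test of the primary endpoint and says nothing on how failures are scored.

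The passages that decide what happens around failure are these:

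- **9.f, ROM+DEX:** "it would be considered treatment failure if platelets are lower than 30x10⁹/L after 4 weeks with romiplostim at 10 mcg/kg/week", or if rescue is needed to hold that level at that dose.
- **9.f, DEX:** the same platelet threshold, judged after three cycles. A further rule for refractory bleeding applies in both arms and is not tied to the number of cycles.
- **9.b, item 3:** "Otherwise, if platelets are lower than 50x10⁹/L treatment with romiplostim will go on until Day 365 since randomization". No exception is made for a declared failure.
- **9.i:** "The following medications are not permitted during this study. After treatment failure, they will be allowed". The list includes other thrombopoietin receptor agonists, rituximab, cytotoxic agents and splenectomy. The sponsor must be told of such use and may, but need not, end study medication.
- **8.b and 8.c:** lack of response is a reason to stop study treatment, and treatment failure is a reason for removal from the study. Yet all subjects are to be followed for at least 6 months after stopping.

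**The concern.** The endpoint looks only forward from the end of study treatment, so what happened before that date does not count. In ROM+DEX, failure is declared while romiplostim may still be running. Salvage given then, and finished before romiplostim stops, lies outside the period that the definition inspects. A durable remission produced by second-line therapy could be credited to romiplostim.

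In DEX, the platelet rule comes into play only after study treatment has ended. The same salvage then falls inside the 180 days and makes the patient a non-achiever. Similar clinical courses can thus be scored differently by arm, and the difference favours the experimental arm. In an open-label trial, the order in which a site stops romiplostim and starts salvage could settle a patient's primary outcome.

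**Working it through.** **Planned sample size (11.b).** The plan says: "A total of 63 patients/arm are required to achieve 80% power to detect a difference with a two-sided significance level of 5" per cent, if the true rates "are 30% in the DEX arm and 56,6% in the ROM + DEX arm and assuming a dropout rate of 15" per cent. Allocation is 1:1. With the pooled-variance formula:

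n = [1.96·√(2·0.433·0.567) + 0.8416·√(0.30·0.70 + 0.566·0.434)]² / 0.266² = (1.373 + 0.568)² / 0.0708 ≈ 53.3, so 54 per arm.

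Allowing for 15% dropout, 54/0.85 gives 64 and 54 × 1.15 gives 63. The stated 63 reproduces, and this point does not change it.

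**Timeline in ROM+DEX (9.b, 9.f).** Starting at 3 mcg/kg on Day 1 and rising by 1 mcg/kg a week, 10 mcg/kg takes seven steps: Day 1 + 7 × 7 = Day 50. Four weeks at that dose gives Day 50 + 28 = Day 78 as about the earliest platelet-rule failure. From there to Day 365 is 365 − 78 = 287 days. This is a maximum, for a patient escalated without interruption who fails at the first opportunity. Table 3 follows this arm to Month 24, so 180 days after Day 365 would be observed.

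**Timeline in DEX (9.b, 9.f).** With cycles starting k days apart, the last dose of the third cycle is on Day 1 + 2k + 3: Day 32 for k = 14 and Day 60 for k = 28. Platelet-rule failure comes after that. Taking cessation as the last study dose, prompt salvage falls within the 180 days. Only the refractory-bleeding rule could produce a failure, and salvage, before a later cycle.

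**Illustrative size.** Inputs:
- 63 per arm, and a true success rate of 30% in both arms (no real difference).
- A share f of ROM+DEX patients fails. The only romiplostim failure rate in the document is 11.5% (18 of 157), in section 5.a.iv, from an earlier 52-week trial in another population. 5% and 20% are assumed as a range.
- A share s of those failures scores as successes. The document gives no figure; 30% and 50% are assumed.
- No such successes in DEX.

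The ROM+DEX rate rises by f × s. At 11.5%, 63 × 0.115 = 7.2 failures, of whom 2.2 to 3.6 would score as successes. The probability of a significant chi-square result favouring ROM+DEX comes from exact binomial enumeration of the uncorrected test at two-sided 5%:

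| f | s | Gain f × s (points) | ROM+DEX rate as scored | P(significant, favouring ROM+DEX) |
|---|---|---|---|---|
| 0 | – | 0 | 30.0% | 2.5% |
| 5% | 30% | 1.5 | 31.5% | 3.8% |
| 5% | 50% | 2.5 | 32.5% | 4.9% |
| 11.5% | 30% | 3.45 | 33.45% | 6.1% |
| 11.5% | 50% | 5.75 | 35.75% | 10.2% |
| 20% | 30% | 6.0 | 36.0% | 10.7% |
| 20% | 50% | 10.0 | 40.0% | 22.0% |

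With 53 per arm (63 × 0.85, rounded down), the two 11.5% rows give 5.9% and 9.5%, against 2.6% with no gain.

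The table supposes that every failure stays in the study and on romiplostim while salvage is given. If only half did, the 11.5% gains would halve to about 1.7 and 2.9 points.

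**The case against.** The strongest reply is that the route rests on silence. A declared failure must stay in the study, stay on romiplostim, receive second-line therapy alongside it, finish that therapy first, and then hold for 180 days. No section says that this will happen. Section 8.b lists treatment failure as a reason for removal and lack of response as a reason to stop treatment. Section 9.i lets the sponsor end study drug after a prohibited medication. Section 9.f refers failures to the Steering Committee. The opening word of 9.b item 3 can be read as covering only patients who do not qualify to stop after the taper. If romiplostim stops at failure, ROM+DEX is scored like DEX. The bleeding clause, whose time window is not stated, might catch some failures too.

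Much of this stands, and it limits the size of the problem. It does not close the gap. Section 8.c follows all subjects for at least 6 months after stopping, 9.i regulates medication after failure, and stopping study drug there is discretionary. The document therefore points both ways.

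A reader might infer that a salvaged failure can never score in DEX. That is too strong. The refractory-bleeding rule applies in both arms, so a narrow route exists in DEX before about Day 60. If treatment cessation were read as the end of any ITP treatment, salvaged DEX failures could score more widely.

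It could also be said that scoring of failures belongs in the statistical analysis plan. Here, however, the protocol itself fixes who is a success, and a later plan that excluded failures would be changing that definition.

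**Conclusion.** The concern holds in a limited form. As worded, the four SROT definitions do not count a declared failure, or earlier non-protocol ITP therapy, as non-achievement. A ROM+DEX failure who remains in the study on romiplostim and remits after salvage can meet 6mSROT-50. The route is essentially confined to that arm: up to 287 days there, against a narrow bleeding-rule route before about Day 60 in DEX. Whether it is open in practice depends on sections that contradict each other.

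The size is illustrative. At 11.5% failure and 30-50% of failures scored as successes, the gain is about 3.5-6 points, and the chance of a false result favouring ROM+DEX is about 6-10% instead of 2.5%. It is lower if failures are removed or romiplostim is stopped. A reader who takes 75% as the share of failures remitting after salvage would get 0.115 × 0.75 = 8.6 points and about 17.5%. The document gives no basis for that share, nor for treating the failure rate of another population, under a definition not given here, as the rate under 9.f. The direction of the bias is firmer than its size.

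**What to change.** 1. Define treatment cessation as the last dose of assigned study treatment.
2. Add to 6mSROT-50, 6mSROT-30, 12mSROT-50 and 12mSROT-30, for both arms: a patient who meets treatment failure (9.f), or receives any ITP treatment other than assigned study drug and 9.e rescue, at any time from randomisation to the end of the relevant off-treatment period, is counted as not achieving SROT. This includes patients removed from the study for failure. The existing bar on all ITP and rescue treatment after cessation stays. The end point matters: 9.f also labels as failures DEX patients who lose response and switch, and one who does so after completing 180 days has already met the 6-month endpoint.
3. Reconcile 8.b, 8.c, 9.b item 3, 9.f and 9.i on whether study treatment and follow-up continue once failure is declared. That clinical choice is the sponsor's.

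The cost is one definition, one sentence and the reconciliation of these sections. Treatment failure is already an outcome. Table 3 already schedules ITP medication to Month 12 and concomitant medication to the end of study. The planned 63 per arm is unchanged, because 30% and 56.6% are inputs. The downside is that the observed ROM+DEX rate may be slightly lower.
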